6.2.3 Molecular response

- 1. Major (MMR): BCR-ABL/ABL ratio ≤ 0.02%
- 2. Complete: Undetectable BCR-ABL

7. Pharmacokinetic and Pharmacodynamic Methods

7.1 Pharmacokinetic Methods

7.1.1 Blood Collection

On Days 1 of Cycle 1, PK blood samples will be obtained pre-dose, 0.5, 1, 1.5, 2, 4, 6 and if possible, 8 hours after administration of the morning dose of the study medication. PK samples will also be obtained pre-dose on Day 1 of Cycles 2 and 3. The exact date and time of the PK blood draws will be recorded along with the date and time of the last dose of study medication preceding the blood draw.

See Appendix F for specific information regarding the procedures for PK blood sample collection, processing and shipment.

7.1.2 Bioanalytical Methodology

The plasma samples will be analyzed for INCB018424 by a validated LC/MS/MS assay, carried out by Incyte Corporation (Wilmington, DE) or Incyte's designee.

7.1.3 Population Pharmacokinetic Analysis

The limited amount of plasma concentration data from this study, will be pooled with the results of a Phase 1 study in healthy volunteers to perform the population PK analysis. If there is sufficient demographic diversity in the population, an attempt will be made to evaluate the effect of demographic characteristics and baseline characteristics (e.g., age, weight, sex, race, renal function, smoking history, etc.) on the population PK profile.

7.2 Pharmacodynamic Method

7.2.1 Blood Collection

On Day 1 of Cycle 1 (at pre-dose and 2 hours after dose), and on Day 1 of Cycles 2 and 3 (pre-dose sample only) venous whole blood samples will be obtained for both whole blood and plasma PD markers according to the Study

calendar. Collection of a plasma PD sample will be done on Day 1 of subsequent cycles as described in Section 5.2. The exact date and time of the blood draws will be recorded along with the date and time of the last dose of study medication preceding the blood draw.

See Appendix F for specific information regarding the procedures for PD blood sample collection, processing and shipment.

7.2.2 Pharmacodynamic Analysis

The whole blood PD samples will be evaluated both unstimulated and following stimulation with a cytokine (e.g., IL-6) to activate the JAK/STAT pathways and then analyzed for both basal and activated levels of JAKs and STATs, including phosphorylated STAT3 and STAT5. Phosphorylated STAT3 and STAT5 will be measured using phospho-specific STAT3 and STAT5 ELISAs. For each patient, the percent inhibition of phosphorylated STAT3 and/or STAT5 will be calculated by comparing predose values with values obtained at different times after dosing. Additional PD markers (e.g., monitoring other cell signaling pathways, measuring specific cell populations or measuring cell surface markers that can be measured by flow cytometry, Western blot or ELISA) may be evaluated utilizing excess whole blood PD samples.

In addition, using the plasma PD sample, changes in plasma cytokine levels and markers of disease activity will be monitored over time using specific ELISAs. For each patient, the percent change in level will be calculated by comparing predose values with values obtained at different times after dosing. Additional PD markers (e.g., other cytokine levels, chemokine levels or other non-genomic protein markers that can be measured by Western blot or ELISA) may be evaluated utilizing excess PD or PK samples. These analyses will be carried out by Incyte Corporation (Wilmington, DE) or Incyte's designee.

7.3 Bone Marrow Aspiration, Biopsy and Cytogenetics

Bone marrow aspiration or biopsy will be taken pre-dose during the screening phase and at Day 1 ± 7 days of Cycle 4, Day 1 of Cycle 7 ± 7 days and thereafter on Day 1 ± 7 days of each 6th subsequent cycle. This includes staining and determination of cytogenetics if abnormal prior to therapy.

7.3.1 Bone Marrow Assessment

The bone marrow biopsy or aspirate should be assessed by an experienced hematopathologist using his/her standard examination. Bone marrow evaluation will include staining, cytogenetics if abnormal prior to therapy and mutation analysis if present prior to therapy.

7.3.2 Cytogenetics

Cytogenetic studies will be repeated only in patients with abnormalities at baseline on Day 1 of Cycle 4, Day 1 of Cycle 7 and thereafter on Day 1 of each 6th subsequent cycle. This will be generally done on the bone marrow samples provided at the defined time points but may also be done on peripheral blood collected at these time points in the event bone marrow aspirate could not be obtained. The cytogenetic testing laboratory will provide specific instructions to the Investigators.

8. REGULATORY AND REPORTING REQUIREMENTS

Adverse event reporting will be as per the current NCI criteria and the MDACC Adverse Event Reporting Policy for Leukemia Phase I and early Phase II studies.

The descriptions and grading scales found in the revised NCI Common Terminology Criteria for Adverse Events (CTCAE) version 3.0 will be utilized for adverse event reporting. (http://ctep.cancer.gov/reporting/ctc.html).

Serious Adverse Event Reporting (SAE)

A serious adverse event is – any adverse drug experience occurring at any dose that results in any of the following outcomes:

- Death
- A life-threatening adverse drug experience any adverse experience that places the patient, in the view of the initial reporter, at immediate risk of death from the adverse experience as it occurred. It does not include an adverse experience that, had it occurred in a more severe form, might have caused death.
- Inpatient hospitalization or prolongation of existing hospitalization
- A persistent or significant disability/incapacity a substantial disruption of a person's ability to conduct normal life functions.
- A congenital anomaly/birth defect.

Important medical events that may not result in death, be life-threatening, or require hospitalization may be considered a serious adverse drug experience when, based upon appropriate medical judgment, they may jeopardize the patient or subject and may require medical or surgical intervention to prevent one of the outcomes listed in this definition. Examples of such medical events include allergic bronchospasm requiring intensive treatment in an emergency room or at home, blood dyscrasias or convulsions that do not result in inpatient hospitalization, or the development of drug dependency or drug abuse (21 CFR 312.32).

- Important medical events as defined above, may also be considered serious adverse events. Any important medical event can and should be reported as an SAE if deemed appropriate by the Principal Investigator or Sponsor.
- All events occurring during the conduct of a protocol and meeting the definition of a SAE must by reported to the IRB in accordance with the timeframes and procedures outlined in "University of Texas M. D. Anderson Cancer Center Institutional Review Board Policy". SAEs must be reported to the IRB and the Sponsor (Safety Project Manager) regardless of attribution.
- All life-threatening or fatal events with possible, probable or definite attribution
 to the study drug must have a written report faxed within 24 hours (next working
 day) of knowledge of the event to the Safety Project Manager in the Office of
 Research Education and Regulatory Management (ORE&RM) ([contact]). The sponsor representative should be notified by phone at [contact]
 to confirm receipt of the fax.
- The MDACC Internal Adverse Event Reporting Form will be used for reporting to the IRB and the Sponsor (Safety Project Manager ORE&RM).
- Serious adverse events will be captured from the time the patient signs
 consent until 30 days after the last dose of drug. Serious adverse events
 must be followed until clinical recovery is complete and laboratory test
 have returned to baseline, progression of the event has stabilized, or there
 has been acceptable resolution of the event.
- Additionally, any serious adverse events that occur after the 30 day time period that are related to the study treatment must be reported to the IRB and the Sponsor (Safety Project Manager ORE&RM). This may include the development of a secondary malignancy.

Reporting to FDA:

 Serious adverse events will be forwarded to FDA by the Sponsor (Safety Project Manager ORE&RM) according to 21 CFR 312.32.

It is the responsibility of the PI and the research team to ensure serious adverse events are reported according to the Code of Federal Regulations, Good Clinical Practices, the protocol guidelines, the sponsor's guidelines, and Institutional Review Board policy.

8.1 Expedited Adverse Event Reporting

Leukemia associated symptoms are not to be reported as adverse events on this protocol. Myelosuppression and associated complication are expected events during leukemia therapy and are part of the treatment success (marrow emptying of leukemia cells). Therefore, myelosuppression and associated complications such as fever, infections, bleeding, and related hospitalization will be reported in the study summary. Only prolonged myelosuppression, as defined by the NCI criteria specific for leukemia, i.e. marrow cellularity <5% on day 42 or later (6 weeks) from start of therapy without evidence of leukemia, will be reported as an SAE and considered in defining the maximum tolerated dose (MTD) and dose-limiting toxicity (DLT). Admission to the hospital for administration of a new cycle of treatment does not require expedited reporting. SAEs occurring in patients registered to the trial but not receiving any protocol agents (ie occurring before protocol treatment) do not require expedited reporting.

For this protocol, the following adverse events are specifically excluded from expedited AE reporting:

			Hospitalization/	
CTCAE Category	Adverse Event	Grade	Prolongation of Hospitalization	Comments
Blood/Bone marrow/ Infection	↓Hemoglobin, leukocytes (total WBC), lymphopenia, ↓neutrophils/ granulocytes (ANC/AGC), ↓ platelets, fever, sepsis	1-4	Yes	Do not require expedited reporting
				Hospitalization for grade
Gastrointestinal	Diarrhea, nausea, vomiting, stomatitis	1-3	Yes	3 AEs does not require expedited reporting Do not require
Metabolic/laboratory	↓K,↓Mg, ↓Na, ↓glucose, ↑K, ↑Mg, ↑glucose, ↑uric acid,↑LDH Or other metoablic indeces	1-4	Yes	expedited reporting unless hospitalized for management

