4.2 Administration of INCB018424

This is an open label, non-randomized, study of INCB018424, administered orally to patients with relapsed/refractory AML, ALL, and MDS (including CMML), and blast phase or tyrosine kinase refractory CML. The study of INCB018424 in each disease listed will be conducted in two parts. The first part is intended to enroll a maximum of 10 patients within each of the four disease categories included in this study and to identify whether significant benefit is observed. If a minimum of one patient shows benefit that is considered significant, there will be an expanded cohort of 20 additional patients treated in that arm of the study.

Patients will receive 50 mg/day administered orally in two divided doses (i.e., BID: every 12 hours \pm 2 hours). Within each arm of the study, three patients will be initially treated and observed for toxicity for one treatment cycle (28 days) before the additional seven patients are entered. Dose reduction will be considered if the number of patients experiencing grade 3 or higher toxicities exceed 2/3, 3/4, 4/7, 5/10, 6/14, 7/18, 8/22, 9/26. Treatment will be administered primarily on an outpatient basis, but can be administered as an inpatient if the patient is hospitalized for other reasons.

The 5 mg tablets have been shown to be stable when stored up to one month at 25° C/60%RH and 40° C/75%RH; the 25 mg tablets have been shown to be stable when stored for three months at 25° /60%RH and 40° /75%RH. (25° C = 77° F, 40° C = 104° F).

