9.3.1 Adverse Events

Severity of adverse events will be based on the NCI–CTCAE v3.0 (NCI Common Terminology Criteria for Adverse Events, Publ. Aug 9, 2006). The subset of adverse events that are considered by the Investigator to have a possible or probable relationship to study medication will be considered to be treatment-related adverse events. If the Investigator does not specify the relationship of the adverse event to study medication, the adverse event will be considered to be treatment-related. The incidence of adverse events and treatment-related adverse events will be tabulated.

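### Section 8.1, read literally, keeps leukemia-associated symptoms out of adverse event reporting, which conflicts with the Section 8 rule for serious events and understates the all-event table in 9.3.1

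*Combined protocol and SAP*

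**What the plan says.** Four parts of the protocol bear on this.

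- **Section 8.1** (Expedited Adverse Event Reporting) begins: "Leukemia associated symptoms are not to be reported as adverse events on this protocol". It does not define leukemia-associated, compare with baseline or provide for adjudication. Myelosuppression is given its own route: "myelosuppression and associated complications such as fever, infections, bleeding, and related hospitalization will be reported in the study summary". Leukemia-associated symptoms are given no such route.
- **Section 8** covers serious events: "All events occurring during the conduct of a protocol and meeting the definition of a SAE must by reported to the IRB", and "SAEs must be reported to the IRB and the Sponsor (Safety Project Manager) regardless of attribution". One of the listed outcomes that make an event serious is "Inpatient hospitalization or prolongation of existing hospitalization".
- **Section 9.3.1** plans two tabulations: "The incidence of adverse events and treatment-related adverse events will be tabulated". The first is of all events, the second of those considered related.
- **Section 4.2** gives the setting: "This is an open label, non-randomized, study of INCB018424".

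**The concern.** An all-event tabulation shown beside a treatment-related one is useful because the first should not depend on anyone's view of cause. If symptoms judged leukemic never become adverse events, the first table has already been filtered by attribution, and the gap between the two tables no longer shows what was set aside. In patients with active leukemia, symptoms such as fatigue, pain, weight loss or dyspnea can come from drug or disease, and the investigator has neither blinding nor a control arm to help separate them.

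Safety and tolerability is the first secondary objective in Section 1. A site that faces a serious leukemia-associated event would also hold two opposing instructions on whether to report it.

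**Working it through.** The point rests on no figure in the plan, so the check is a comparison of the texts, followed by a sensitivity calculation on assumed rates.

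**1. Scope of the 8.1 sentence.** It applies to adverse event reporting on the protocol and carries no limit to expedited reports. Elsewhere in 8.1, hospital admission for a new cycle, serious events before any protocol agent is given, and the listed table items are each tied to expedited reporting. The section heading points the same way. The sentence therefore has a literal broad reading and a plausible narrow one, and the text does not choose between them.

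**2. Serious events.** Take a patient hospitalized for a symptom judged leukemic.
- Section 8: hospitalization makes the event serious, and it is reportable whatever its attribution. Capture starts at consent, before any drug is given, so it does not depend on drug causation.
- Section 8.1, literal reading: the symptom is not reported as an adverse event.

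Both instructions cannot be followed.

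**3. Non-serious events.** For these, Section 8 points only to NCI criteria and an institutional policy, neither of which is in the documents, so there is no direct contradiction. The effect is on the analysis. A symptom excluded from adverse event reporting enters neither tabulation in 9.3.1. Leaving it out of the treatment-related table is consistent with the investigator's judgement; leaving it out of the all-event table is not consistent with that table's purpose.

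**4. Direction and size.** Let p be the true proportion of patients with at least one adverse event, and s the share of those patients whose only events are classed as leukemia-associated. Then

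tabulated incidence = p × (1 − s); patients missing from the table = n × p × s.

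Both p and s are assumptions. Only n = 30, the full size of a disease category in 9.1.1, comes from the plan.

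| p | s | Tabulated incidence | Missing, of 30 |
|---|---|---|---|
| 0.30 | 0.10 | 0.27 | 0.9 |
| 0.30 | 0.50 | 0.15 | 4.5 |
| 0.50 | 0.10 | 0.45 | 1.5 |
| 0.50 | 0.50 | 0.25 | 7.5 |
| 0.70 | 0.10 | 0.63 | 2.1 |
| 0.70 | 0.50 | 0.35 | 10.5 |

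For any s above zero the tabulated value lies below p, so the direction follows from the rule. The spread, from about 1 patient to about 10 of 30, reflects only the range assumed. The documents supply nothing to narrow it.

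**The case against.** The strongest reply is that 8.1 concerns expedited reporting throughout. Its heading says so, and it uses the word reported loosely: the myelosuppression sentences also omit the word expedited, although the table below them excludes cytopenias, fever and sepsis from expedited reporting only. The narrow reading is therefore reasonable, and the unqualified wording does not prove that a full exclusion was intended. Even so, a site can follow the sentence as written, and the same rewording is needed under either reading.

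It can also be argued that Section 8 defines a serious event as an adverse drug experience, which would leave leukemic symptoms outside it. Reporting whatever the attribution, from consent onward, does not fit that argument well.

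A reader might infer more than the documents support:

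- **That nothing is recorded or recoverable.** The study calendar in 5.2 requires weekly review of constitutional symptoms and examination in cycle 1, the visit lists in 5.2.1 and 5.2.2 include medical history, and 5.2.4 has monthly contacts about symptoms documented in the medical record and, as appropriate, the case report form. What these do not guarantee is a graded and attributed adverse event.
- **That the missing-attribution default in 9.3.1 is defeated.** That rule reads: "If the Investigator does not specify the relationship of the adverse event to study medication, the adverse event will be considered to be treatment-related". A symptom judged leukemic has been attributed, so the default would not apply to it in any case.
- **That all-cause incidence is the only safety measure free of attribution.** Laboratory abnormality incidence and shift tables (9.3.2), vital signs (9.3.3), survival (9.4.1) and time to treatment failure (9.4.3) do not turn on the investigator's view of cause.
- **That the early-death categories in 9.5.2 lose their record.** The 8.1 sentence concerns symptoms; death is a serious outcome under Section 8, and 9.5.2 assigns its category separately.

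The practical consequences are also bounded. Safety analysis is descriptive (9.3), the cohort stopping rule counts only toxicity thought directly related to the drug (4.1 and 9.1.1), and without a control arm the issue is under-ascertainment, not bias between groups.

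**Conclusion.** The point holds in a limited form. Read literally, 8.1 contradicts Section 8 for serious leukemia-associated events, and it makes the all-event incidence in 9.3.1 too low by leaving out non-serious symptoms that the investigator attributes to disease. The second effect rests on two assumptions: that sites apply the sentence as written, and that the institutional policy named in Section 8, which is not available here, does not require such symptoms to be recorded as adverse events anyway. The direction is downward; the size cannot be estimated from the documents. If only expedited reporting was meant, the defect is one of wording and the incidence need not be affected. The response analysis and the cohort stopping rule do not depend on this point. The sentence should be corrected because it bears on the first secondary objective and the correction is small.

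**What to change.** Replace the opening sentence of 8.1 with wording to this effect: *New symptoms, and symptoms that worsen from their baseline grade, are recorded as adverse events with grade, dates and attribution even when judged due to leukemia; if so judged, they are exempt from expedited reporting only.*

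In 9.3.1, state that the all-event table uses every recorded adverse event, including those attributed to disease, and that the treatment-related table is produced separately.

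Reconcile 8.1 with Section 8 by stating how a serious event attributed to leukemia is reported to the IRB and the sponsor, so that a site has one instruction.

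The cost is additional case report form entries and an all-event table that is longer and looks less favourable. Adverse events are already assessed weekly in cycle 1 and at scheduled visits afterwards (study calendar, 5.2), so no visit or procedure is added.

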9. STATISTICS

9.1 Study Population

All patients who received at least one dose of study medication will be included in the safety analyses.

9.1.1 Selection of Sample Size

This phase II study will use a Gehen's design. Assuming a null response rate of 0%, targeting a 15% response rate and power=80%, the trial will initially enroll 10 patients in each disease category: 1) AML; 2) ALL; 3) MDS; and 4) CML. If at least one response is achieved in the 10 patients in a disease

Category, then a total of 30 patients will be enrolled in this disease category. Thirty patients will provide a confidence interval for response rate with half-width=0.13, assuming the true response rate is 15%. The total sample size is 120.

For toxicity evaluation, patients enrolled in the study will be considered in 2 cohorts (I) those with relapsed/refractory AML, ALL, and MDS (including CMML), and blast phase CML, and (II) those with chronic phase CML. At any time after 6 patients are enrolled in cohort I (including AML, ALL, MDS, blast phase CML patients), if 30% or more patients experience grade 3 or 4 toxicity thought to be directly related to INCB018424 and lasting longer than 2 weeks, then we will stop that cohort of the trial. At any time after 6 patients are enrolled in cohort II (including chronic phase CML patients), if 15% or more patients experience grade 3 or 4 toxicity thought to be directly related to INCB018424 and lasting longer than 2 weeks, then we will stop that cohort of the trial.

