9.2.1 Efficacy and PK/PD Analysis

Efficacy analyses will be exploratory in nature. All efficacy measures will be estimated with 95% confidence intervals at the dose used in the expanded cohort. The clinical response and the hematological response will be estimated with 95% confidence intervals at each time point. The response rates over time may be analyzed graphically or using a statistical model.

The PK parameters of INB018424 will be summarized using descriptive statistics, and the log-transformed INCB018424 PK parameters will be compared using a 1-factor analysis of variance. The mean values of the PK parameters may be compared to historical data in healthy volunteers to determine if the INCB018424 PK profile is different between patients with hematological malignancies and healthy patients.

For each patient who has taken study medication, the PD parameters will be calculated to explore preliminary evidence of PD activity by assessing the

effect of INCB018424 on pre- and post-dose. If the p-STAT3/5 signaling data are sufficiently robust, an exploratory PK/PD analysis will be performed.

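### In arms that expand, the pooled response rate over 30 patients is biased upward by the one-response gate, and the analysis section makes no allowance for it

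*Combined protocol and SAP*

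**What the plan says.** Section 9.1.1 sets a two-stage Gehan-type design, with a null response rate of 0%, a target of 15% and 80% power. For stage 1, "the trial will initially enroll 10 patients in each disease category". The gate begins "If at least one response is achieved in the 10 patients in a disease"; an arm that meets it is enlarged to 30 in all. Section 4.2 gives the same numbers from the other side: "there will be an expanded cohort of 20 additional patients treated in that arm of the study".

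On precision, section 9.1.1 says: "Thirty patients will provide a confidence interval for response rate with half-width=0.13", for a true rate of 15%. It gives neither the interval method nor the confidence level beside that figure.

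On analysis, section 9.2.1 says: "All efficacy measures will be estimated with 95% confidence intervals at the dose used in the expanded cohort". It also describes the efficacy analyses as exploratory. It names no interval method, and no estimator or interval that takes account of the stage 1 gate.

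**The concern.** The precision statement treats an expanded arm as a plain sample of 30. It is not one: stage 1 results with no responders have been removed before the arm can reach 30. If the 10 stage 1 patients are pooled with the 20 expansion patients and the simple proportion is reported, the selection passes into the estimate.

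The gate is easy to pass, so weakly active arms can expand, and in those arms the inflation is largest relative to the truth. Observing anti-tumor effect is the primary objective (section 1) and the plan offers estimation rather than a final test, so these rates are the main output of the trial. A reader deciding which disease deserves further study would compare them at face value.

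**Working it through.** **Inputs.** Stage 1 has 10 patients, expansion needs at least 1 response, and the total is 30 (section 9.1.1). Stage 2 has 20 patients (section 4.2). The 95% level comes from section 9.2.1 and is assumed to be two-sided and to apply to the 0.13.

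**Step 1: reproduce the plan's figures.**
- Chance of at least one response in 10 at 15%: 1 − 0.85^10 = 0.803, which matches the 80% power.
- Normal-approximation (Wald) half-width: 1.96 × √(0.15 × 0.85 / 30) = 0.128, which rounds to 0.13.
- The Wilson half-width at 4.5/30 is 0.127, which also rounds to 0.13. The figure therefore does not reveal which method is intended.

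**Step 2: expected pooled rate given expansion.** Let X1 ~ Bin(10, p) and X2 ~ Bin(20, p), with expansion if X1 ≥ 1. Then

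P(expand) = 1 − (1 − p)^10, and E[x/30 | expand] = (10p / P(expand) + 20p) / 30.

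At p = 0.05: P(expand) = 1 − 0.95^10 = 0.401, and (0.5/0.401 + 1)/30 = (1.246 + 1)/30 = 0.075.

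| True rate | P(expand) | Expected x/30 given expansion | Bias (points) |
|---|---|---|---|
| 2% | 18% | 5.0% | +3.0 |
| 5% | 40% | 7.5% | +2.5 |
| 10% | 65% | 11.8% | +1.8 |
| 15% | 80% | 16.2% | +1.2 |

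The 20 expansion patients have expected rate p whatever stage 1 showed, so their rate alone carries no such bias.

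**Step 3: precision at 15%, given expansion.** The standard deviation of x/30 is 0.062, against 0.065 for a fixed sample of 30. The expected half-width is 0.128 (Wald), 0.127 (Wilson) and 0.141 (Clopper-Pearson). Coverage is 97.1%, 96.6% and 98.8% respectively.

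**Step 4: does the choice of interval matter?**
- Wald lower limits at 1, 2 and 3 responses in 30 are −0.031, −0.023 and −0.007.
- Wilson coverage given expansion is 83% at a true 3% and 87% at 5%.
- Clopper-Pearson coverage given expansion is 91% at a true 2%, 96% at 3% and at 5%, and 99% at 10% and at 15%.

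**Step 5: cost of the expansion-only row.** With 20 patients at a true 15%, the expected Clopper-Pearson half-width is 0.167.

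**The case against.** The strongest reply has four parts.

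- **Direction of the bias.** It is upward only given expansion. If stopped arms are counted as 0/10, the average estimate at a true 15% is 0.803 × 16.2% = 13.0%, which is too low. This stands, and the point must be worded conditionally. It does not remove the point, because a 30-patient rate exists only for arms that expanded.
- **Size.** At the design rate the bias is 1.2 points, less than a tenth of the half-width, and efficacy is exploratory. An arm with a true rate of 2% expands only 18% of the time. This stands and makes the point minor.
- **Precision.** A reader might infer from the two-stage selection that 0.13 overstates the precision. The documents do not support that. The figure is stated for a true 15%, where it is correct; the conditional spread is slightly smaller than in a fixed sample, and Wald and Wilson half-widths stay at 0.13. The 0.141 arises only if the more conservative exact interval is chosen. Nor can one say that the plan has committed itself to Wald, since Wilson fits equally well and no method is named.
- **The exact interval does not remove the selection.** Given expansion, its coverage still falls to 91% at a true 2%. This stands. The separate expansion-patient row deals with the selection; naming the interval is secondary.

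**Conclusion.** The concern holds in a limited form. In expanded arms the pooled rate is biased upward, by 2.5 points at a true 5% (half as much again as the truth), 1.8 at 10% and 1.2 at 15%, and section 9.2.1 makes no allowance for it. The 0.13 is not an error, and precision at 15% is not overstated. Severity is minor.

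This rests on four assumptions: the gate and the reported rate use the same definition of response; both stages share one true rate; expanded arms reach the full 30; and the reported rate pools both stages. The last is read from the 30-patient precision statement in section 9.1.1, since section 9.2.1 does not spell it out.

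**What to change.** In section 9.2.1, for each arm that expands:

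1. Beside the pooled x/30, report the response rate and exact 95% interval in the 20 expansion patients alone. A two-stage-adjusted estimate, such as the uniformly minimum-variance unbiased estimator, is an alternative.
2. State that the pooled rate is conditional on at least one response in stage 1.
3. Name the exact (Clopper-Pearson) interval, which avoids negative limits at 1 to 3 responses and covers better than Wilson at true rates of 3% to 5%.

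If the exact interval is adopted, add to section 9.1.1 that its expected half-width is about 0.14 at a true 15%. This follows from the choice of method and does not correct the 0.13.

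The cost is a few sentences and one extra row per expanded arm. That row is wider (expected exact half-width about 0.17 at 15%) because it sets aside a third of the patients, so it belongs beside the pooled rate and should not replace it. Neither the design nor the sample size changes.
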